6.2. RCT eligibility criteria

Trial inclusion criteria (all criteria must be met):

- 1) Aged 12 months to <10 years
- 2) Presenting within 1 week of suspected AOM onset (other preceding respiratory tract infection symptoms may be longer)
- 3) Parent/legal guardian available to give consent
- 4) Parent-reported ear pain in 24 hours pre-enrolment (or parent-suspected pain if child too young to report pain)
- 5) Clinician diagnosis of acute otitis media (although not an entry criterion, clinicians will be asked to report the presence of otoscopic evidence of acute tympanic membrane inflammation, operationalised as per our previous trial⁶ as: erythema with dullness or cloudiness; or bulging)
- 6) Child is immunocompetent.
- 7) Clinician willing to use a NICE-recommended 'no' oral antibiotic prescribing strategy or a 'delayed' oral antibiotic prescribing strategy (as per NICE guidelines) for the AOM and other elements of the underlying acute respiratory tract infection. NICE recommends a 'no' or 'delayed' antibiotic prescribing strategy for most immune-competent children with acute otitis media.
- 8) Parent able to give ear drops.

- 9) Parent willing in principle to use ear drops before oral antibiotics and to wait before giving delayed antibiotics as per NICE guidelines.
- 10) Parent able to report the child's ear pain.
- 11) Parent able and willing to complete daily Symptom and Recovery Questionnaire in the English language, and receive regular follow-up telephone calls, in the English language, today and every 2-3 days for up to 7 more days (or until child has been free of ear pain without medicines for two days running).

Trial exclusion criteria (presence of any warrants exclusion):

- 1) Child requires immediate hospitalisation
- 2) Child requires same day oral antibiotic treatment for AOM or other elements of the underlying acute respiratory tract infection (assess these children for observational study eligibility). NICE recommends same day antibiotic treatment for:
 - 2.1) Child younger than 2 years with bilateral acute otitis media
 - 2.2) Otorrhoea (discharge from the ear)

2.3) Child systemically very unwell or showing signs of respiratory distress (e.g. tachypnoea, hypoxia or recession)

2.4) Child has symptoms and signs suggestive of serious illness and/or complications (particularly mastoiditis)

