- 15) Child has a hearing aid and parent feels hearing aid should remain in place in the AOM ear

- 16) Symptoms (i.e. hearing loss and longer duration of illness) more suggestive of a diagnosis of otitis media with effusion (glue ear)
- 17) Child has previously taken part in the CEDAR RCT
- 18) Child has taken part in any research involving medicines within the last 90 days, or any other AOM-related research within the last 30 days

Inclusion of children with learning difficulties or with chronic conditions not contra-indicated by NICE guidelines

Children with severe learning difficulties or at higher risk of AOM (e.g. children with Down's Syndrome and/or cleft palate) whose parents are able to interpret and record ear pain will be included, to maximise generalizability. We are not aware of evidence that AOM is different in these children, and the treating clinician will be responsible for deciding if children are safe to receive delayed antibiotics.

Exclusion of children requiring same day oral antibiotic treatment

For the RCT, only children not requiring same day oral antibiotic treatment will be eligible. In the context of this trial, a 'delayed' antibiotic will mean that both clinician and parent are comfortable in principle to try the drops first and defer antibiotics until (at least) the following day, and (at best) to only administer antibiotics if the child is not improving after three days [[name] BMJ 2001]. The median duration of earache is 3 days [Thompson BMJ 2013] and our hypothesis is that drops will help parents control symptoms during this staggered decision making process. We agree that many (probably most) parents will cash the antibiotic prescription so that it is available to them, but the primary outcome is antibiotic *consumption*.

We have considered whether children requiring same day antibiotics should be eligible for the RCT, and believe they should be excluded for two reasons. Firstly, children who have been prescribed an antibiotic and told to start it immediately have very little opportunity to achieve the primary outcome (not consuming antibiotics by day 7). This risks unduly swamping the trial with children whose parents had no intention of using drops first. Secondly, children requiring same day antibiotics are likely to be more unwell – a safety issue.

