We have given careful consideration to whether children requiring same day antibiotics should be eligible for the OCS, since they are not eligible for the RCT, given that the purpose of the OCS is to assess the external validity of the RCT sample.

On the one hand, we acknowledge that for some clinicians there is likely to be a difference between children whose clinicians are comfortable in using a 'no' or 'delayed' antibiotic prescribing strategy, and children whose clinicians feel that a same day antibiotic is clinically indicated. However, we also acknowledge that for other clinicians, the selection of children for different antibiotic prescribing strategies will be more arbitrary.

On balance, and in discussion with our Trial Steering Committee, we decided to include children whose clinicians opt for a same day antibiotic prescribing strategy since the OCS will then be able to:

- Gain insight into the variability of AOM antibiotic prescribing practices
- Find out what proportion of children given same day antibiotics (which will also be measured in the screening logs)
- Investigate if children receiving same day antibiotics experience a different illness trajectory and pain outcome compared to children receiving 'no' or 'delayed' antibiotics, and hence aid interpretation of the representativeness of the RCT population
- Improve OCS recruitment because fewer children would be ineligible
- Quantify the between-clinician variability in the way in which the delayed and same day antibiotic prescribing strategies are operationalised

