Parents who decline participation or whose children are ineligible for the trial will be invited to take part in an observational study. In all cases trial participation will be invited prior to extending any invitation to take part in the OCS. This is in order to prioritise entry into the RCT. Participation in the RCT would not involve any change in their management, but would involve collecting data about their presentation, management and follow-up. If parents decline participation in the observational study then they will not be entered into the study but we will record anonymous data in a screening log.

Entry into the RCT or OCS

Entry into the RCT or OCS will be signified by the completion of a valid consent form. Parents agreeing to take part in the RCT will be asked to sign a consent form after which the Responsible Clinician will sign the Trial Prescription

and the parent will be given the Patient Pack and, if the child is allocated to one of the two treatment arms of the RCT, the trial medicines. For parents or carers agreeing to take part in the OCS, the parent will be asked to sign a consent form, either while with the Responsible Clinician, or soon after the consultation and before leaving the site. Any patient subsequently found ineligible or declining to participate will be recorded on a screening form with brief reasons for ineligibility or declining, the remaining data destroyed and a protocol deviation recorded.

Online data collection means instant notification of recruitment to the lead Centre (Bristol). For all patients, including patients recruited using paper forms, GP sites will be asked to fax to the Bristol trial centre by the end of the same working day, evidence of valid consent and the parent's contact details. This will trigger a telephone call to the parent (usually on the same or following day) from the CEDAR trial nurse to address any questions or concerns about the trial or trial medicines.

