6.7. Maximising external validity

External validity is a challenge for the CEDAR trial as much as it is for other trials in general, and trials of acute otitis media (AOM) in particular. Indeed, a previous report has estimated that 44% of eligible children with AOM have been recruited to previous RCTs of antibiotics.¹

Three of the above recruitment assumptions will be key to the trial's external validity: (i) the proportion of presenting children invited to participate (this proportion will be monitored by asking sites to use standard diagnostic Read codes (e.g. otalgia and acute otitis media) allowing the study team to estimate presentation rates); (ii) the proportion meeting eligibility criteria (this proportion will be monitored through clinician completed screening logs); and (iii) the proportion of invited children agreeing to participate (this proportion will be monitored through clinician completed screening logs). We propose to carefully record as much information about children as possible in each of these three steps in order to: (i) rectify emerging problems (to maximise external validity) and (ii) measure (so we can report) the extent of the threat to external validity.

Furthermore, we will undertake a parallel observational cohort study to the degree to which children recruited to the CEDAR RCT are representative of the population of potentially eligible children.

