The pain the child suffers is an important outcome for parents and will be a key secondary outcome, comparing whether the active drops are more effective than placebo drops. We will measure pain using the validated zero to 10 numerical rating scale we used in our previous RCT of delayed vs. same day antibiotic for childhood AOM.⁶ This trial showed mean pain scores of around 6.5 (same day antibiotics) and 5.5 (delayed) at 24 hours and overall mean pain scores of 2.6 (same day) and 3.6 (delayed). Regarding the minimum clinically important difference, our PPI group indicated that they would find a 10% (or greater) reduction in pain useful, and the largest difference observed in our previous trial using the same Symptom and Recovery Questionnaire was one point [[name] BMJ 2001]. Again assuming 90% power and α =0.05 we can detect a mean difference of 1 (SD=2.5 based on trial data) in pain score between the active and placebo ear drop groups, with 133 children per arm. Assuming 20% attrition and equal numbers in the three groups, we need 167 children per arm of the trial (more than for the primary outcome) and therefore 501 children in total.

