The key secondary analysis will analyse the difference in pain scores, between the active and placebo groups, 24-36 hours after administration of drops. This information will be collected using the Symptom and Recovery Questionnaire by asking the parents to score their child's ear pain over the past 24 hours on the evening of Day 2. The analysis–will be conducted using linear regression, adjusting for baseline pain score (collected prior to randomisation) and centre. This will be followed by a linear regression model where all other principles described for the primary analysis above will be applied, including the potential mediating effect of antibiotic use and other analgesics on how this might affect the interpretation of the results. Other secondary analyses will use the appropriate regression method, and, as these will be exploratory in nature, the p-value will be presented but will interpreted with due caution. The analysis will be conducted using the statistical package STATA. The trial statistician and senior statistician will be blinded to the different arms of the trial for the main analysis.

At the pre-funding stage, two reviewers identified that the use of antibiotics and analgesics could influence the effect of the ear drops on pain. Although evidence suggests the effects of antibiotics are modest [[name] BMJ 2001], on consideration we agree and will not adjust for post-randomisation health care variables such as analgesics and antibiotics in our main models or when reporting our main results. However as part of secondary sensitivity analyses, we will look at the mediating effect of analgesics and antibiotics to help interpret and contextualise our main findings, with the potential for confounding kept in mind.

We will measure selection bias, model the effects of any selection bias, and provide descriptive data regarding the presentation, management and outcome of children with AOM who are not recruited into a trial. We found evidence that fewer than 44% of eligible children were recruited into AOM trials [Bains 2001] and that the most likely reason for not recruiting was severity. To test this within CEDAR and to inform the assessment of generalisability, we will compare the global illness severity scores, made by parents and clinicians at baseline, across the RCT and OCS.

A full Statistical Analysis Plan will be developed and reviewed by the Trial Steering Committee.

Health economic analysis

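### One RCT-versus-whole-OCS severity contrast serves two purposes: it suits generalisability, but as a test of selection among eligible children it also picks up the trial's exclusion criteria

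*Protocol*

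**What the plan says.** Section 12.5 of the Protocol cites evidence that fewer than 44% of eligible children entered earlier trials in acute otitis media (AOM), and that "the most likely reason for not recruiting was severity". To test this in CEDAR, and also to inform generalisability, "we will compare the global illness severity scores, made by parents and clinicians at baseline, across the RCT and OCS". No subset of the OCS is named. The same section promises to model the effects of any selection bias.

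Section 6.7 gives the OCS a matching target: the degree to which "children recruited to the CEDAR RCT are representative of the population of potentially eligible children".

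The OCS is wider than that target:

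- Section 6.4: "Parents who decline participation or whose children are ineligible for the trial will be invited to take part in an observational study". Section 12.2 says the same.
- Section 6.2, on children who need same-day oral antibiotics and so cannot enter the RCT: "assess these children for observational study eligibility".
- Section 6.3, after discussion with the Trial Steering Committee: "we decided to include children whose clinicians opt for a same day antibiotic prescribing strategy".

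Section 6.2 also gives a reason for keeping this last group out of the RCT: "children requiring same day antibiotics are likely to be more unwell".

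**The concern.** The hypothesis in 12.5 is about eligible children who were not recruited. The comparator is eligible children whose parents declined, mixed with children whom the protocol itself kept out of the RCT. Severity helps to define that second group. RCT exclusions 2.3 and 2.4 remove children who are systemically very unwell or show signs of serious illness, whereas the only comparable OCS exclusion is immediate hospitalisation.

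A higher mean severity in the OCS could therefore be read as evidence that sicker eligible children were passed over when it only restates the exclusion criteria. Real selection among eligible children could also be exaggerated or masked, depending on the mix of children who join the OCS. A selection-bias model built on this contrast would carry the same confusion into objective 5.4.12 (representativeness of the trial sample).

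**Working it through.** **The plan's own figure.** Section 12.1 states "we need 167 children per arm of the trial (more than for the primary outcome) and therefore 501 children in total". For a pain difference of 1.0, SD 2.5, two-sided 5% and 90% power, n = 2 × (1.960 + 1.282)² × 2.5² / 1² = 131.3, so 132 per arm (133 stated, within rounding and method). Then 133 / 0.8 = 166.25, so 167, and 3 × 167 = 501. The synopsis caps the OCS at an equal number. The Protocol gives no figure for the severity comparison itself.

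**What the contrast estimates.** Let f be the share of the OCS that is trial-ineligible, g their mean severity minus the RCT mean, and s the mean severity of eligible decliners minus the RCT mean. Then

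OCS mean − RCT mean = (1 − f) × s + f × g.

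The hypothesis concerns s. With no selection among eligible children (s = 0) the contrast still equals f × g.

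**An illustrative share.** Section 6.5 assumes 0.66 eligible and 0.25 agreeing. If ineligible children and decliners join the OCS at the same rate (an assumption), then

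f = 0.34 / (0.34 + 0.66 × 0.75) = 0.34 / 0.835 = 0.41.

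**Chance of declaring a difference when s = 0.** The gap g is not in the documents, so a range is shown in SD units. Section 12.5 names no test or alpha for this comparison; two-sided 5% is assumed. With n₁ = 501 in the RCT and n₂ in the OCS,

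z = f × g / √[1/n₁ + (1 + f(1 − f)g²)/n₂].

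For f = 0.407, g = 0.3 and n₂ = 501: 0.122 / 0.0635 = 1.92, giving a probability of about 0.49.

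| Gap g (SD) | Bias f × g (SD) | OCS 501 | OCS 250 |
|---|---|---|---|
| 0.1 | 0.04 | 10% | 8% |
| 0.2 | 0.08 | 25% | 18% |
| 0.3 | 0.12 | 49% | 35% |
| 0.5 | 0.20 | 89% | 73% |
| 0.8 | 0.33 | 99.9% | 98% |

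Sensitivity to the share, 501 versus 501: f = 0.1 with g = 0.2 gives 6%; f = 0.1 with g = 0.5 gives 12%; f = 0.34 with g = 0.5 gives 76%; f = 0.7 with g = 0.5 gives about 100%.

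**Check by simulation** (Welch t-test, 4,000 runs, s = 0). With f = 0.34 and g = 0.5 the whole-OCS contrast rejects 77% of the time, and the contrast restricted to eligible OCS children 4.5%. Across all scenarios run, the restricted contrast rejects 4.5% to 5.2%.

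**Precision of the restricted contrast.** 501 × (1 − 0.407) = 297 eligible decliners. The difference detectable with 90% power is 3.24 × √(1/501 + 1/297) = 0.24 SD. With 150 decliners it is 0.30 SD.

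**The case against.** The strongest reply is that the sentence in 12.5 has a second stated purpose. Generalisability, and objective 5.4.12, concern children with AOM in primary care at large, and for that RCT versus the whole OCS is the right comparison. This stands, and the contrast should stay.

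A second reply is that stratification belongs in the analysis plan: 12.5 announces one, and Appendix 7 leaves the representativeness measure to be defined later. That has some force, since nothing forbids a split. But 12.5 does more than stay silent. It ties a particular contrast to a particular hypothesis, and the two do not match. Section 6.3 foresees that same-day-antibiotic children may differ and plans to look at their illness course and pain; it does not separate them in the baseline severity comparison.

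A third reply concerns the obvious remedy. Whether a child requires same-day antibiotics is partly a clinician's judgement, and 6.3 accepts that for some clinicians the choice is rather arbitrary. Severity-driven non-recruitment may act through that decision, so a decliners-only test could hide part of it. This stands and shapes the fix.

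The size is also open to challenge. Section 6.5 calls 66% eligible conservative, because the 34% behind it is bilateral disease at any age while the exclusion covers only under-twos. Some trial-ineligible children are barred from the OCS too, for example those with otitis externa or glue ear. Others, such as those with grommets or a family history of G6PD deficiency, need not be sicker at all. Both f and g may therefore be smaller than illustrated.

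A reader might infer that the planned comparison is bound to show a difference, or that selection among eligible children cannot be studied in CEDAR. The documents support neither. Rejection is a probability that can be as low as about 6%, and the data needed to separate the groups are to be collected.

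**Conclusion.** The point holds in limited form. One contrast is given two jobs and suits only generalisability. As a test of whether severity keeps eligible children out, it is biased by f × g, the ineligible share of the OCS times their severity gap. The Protocol gives the expected direction for same-day-antibiotic children but neither quantity.

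The figures of 25%, 49% and 89% are illustrations. They rest on a 41% share, equal OCS uptake, every ineligible child shifted by the same gap, a full OCS of 501 and an assumed two-sided 5% test. Without any significance test, the estimated difference would still be off by f × g.

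The consequence is confined to the external-validity work and the selection-bias model. The primary and key secondary randomised comparisons and the sample size are untouched.

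**What to change.** In 12.5, or in the analysis plan with a pointer from 12.5:

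1. Keep RCT versus the whole OCS, labelled as the generalisability comparison.
2. Report the baseline severity difference from the RCT, with a 95% CI, side by side for:
   - (a) OCS children who met the RCT criteria but whose parents declined, as the measure of selection among eligible children and the basis for the selection-bias model;
   - (b) OCS children not entered because the clinician chose same-day antibiotics, as their own stratum, since that decision is partly discretionary and may itself carry severity-driven selection;
   - (c) other trial-ineligible OCS children.
3. Define the strata from the eligibility data, planned management and reasons for non-participation that the Protocol already has sites record (6.3, 6.5, 9.4, 10.2, 10.3).
4. Reconcile OCS inclusion criteria 7 and 8 in 6.3 with the rest of the Protocol. They sit in a list of which every item must be met, so read literally they admit only children whose parents declined. The RCT exclusion list in 6.2, the remainder of 6.3, and 6.4 and 12.2 all say otherwise.

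The cost is a change of wording and one stratified table, with no new data collection. The downside is smaller strata: about 297 eligible decliners on the Protocol's rates, still enough for 90% power at about 0.24 SD, and fewer if the OCS falls short of 501.

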13. DATA MANAGEMENT

13.1. Data handling

Custodian: Head of School, Social and Community Medicine, University of Bristol.

The validated clinical database, trial management database and randomisation system will be designed so as to protect patient information in line with the Data Protection Act 1998. Trial staff will ensure that the participants' anonymity is maintained through protective and secure handling and storage of patient information at the trial centres. The participants will be identified only by a patient ID number on the CRF (both on the paper and webbased forms). All documents will be stored securely and made accessible only to trial staff and authorised personnel. The trial will comply with the Data Protection Act 1998 which requires data to be anonymised as soon as it is practical to do so.

Formal SOPs will be developed to detail each element of the data handling procedure.

A summary of the overall trial results will be made available to those parents who have confirmed that they wish to receive them. We will ask for written consent to write (after the completion of the trial, which may be three years later) to parents with a summary of the CEDAR trial results, and for parents whose child was allocated to one of the ear drop groups, further information about (i) whether they thought the child was in the active or placebo group, and (ii) the actual IMP allocation.

13.2. Data management

Data collection, management and archiving will be conducted in accordance with the principles of the Data Protection Act and Good Clinical Practice guidelines. We will use a secure, web-based (RedCap [Harris et al 2009]) data collection platform which will be developed, validated, hosted and supported by the University of Bristol. The system will provide a secure login to allow collaborator authentication and direct data entry, with a full audit trail. The system will also maximise access (from any primary care sites across England and Wales) while minimising risk of data loss, duplication and security lapses from laptops and other portable media. The system will incorporate data entry and validation rules to reduce data entry errors, and management functions to facilitate auditing and data quality assurance. A bespoke web-based system will be developed to maximise the user-friendliness of data entry for clinicians and for parents.

All patients will be consented using paper consent forms, pre-numbered with the Patient ID number, and provided in the Patient Pack. Consent forms will be scanned and linked to the patient's medical record by site staff and sent by secure fax to the Bristol Centre on the day of recruitment, as well as being returned to the Bristol Centre by pre-paid return addressed envelopes.

While on-line data entry will be the default method of data capture, paper-based alternatives will be provided to accommodate clinician preference and allow recruitment to continue in the unusual event of website inaccessibility. Responsible Clinicians will be asked to enter all data onto the website by the end of day zero, except participant registration details, which will be entered by Bristol Centre staff onto an off-line trial management database. Once data are added to the web-based database, all patient paperwork (except consent forms and registration details) will be stored at the primary care site until completion of participant recruitment. Patient identifiers will be kept on a separate system from the clinical data and data protection requirements will be further enforced by best practice trial management procedures. Paper versions saved on site will be archived by the University of Bristol at the end of the trial according to local policy for paediatric clinical trials, with all data retained for at least 15 years post trial closure in line with University of Bristol procedures.

A study management system will also be developed to record the patient identifiable information and assist the study team with the workflow process. This system is developed using MS Access and SQL Server and hosted in the Bristol University data centre. It is secured using Windows network groups and secure remote access is provided using Windows Remote Desktop. The Bristol University data centre is both physically and electronically secure, with clustered servers providing resilience. All databases and network folders are backed up on a daily basis, encrypted and stored securely.

